3.4.3 Standard Safety Other than AEs

Individual subjects’ vital signs outlined in Table 3 of special clinical concern, which align with the Pfizer standard criteria, will be summarized by randomized arm, as part of standard safety-related outputs.

Table 3 Vital Signs to be Monitored

Parameter	Flag Level*	Conventional Units
Systolic Blood Pressure (seated)	< 90	mm Hg
	≥ 30 change from baseline	mm Hg
Diastolic Blood Pressure (seated)	< 50	mm Hg
	≥ 20 change from baseline	mm Hg
Pulse rate (seated)	< 40	bpm
	> 120	bpm

*All flag level changes are cumulative from baseline (defined as result closest prior to dosing at Visit 5 (Day 1))

bpm – beats per minute

In addition Pfizer standard criteria for reporting of cardiac conduction intervals will be summarized by randomized arm.

In addition, changes in background medications related to glycemic control, lipid control, or blood pressure will be summarized as follows, at any time after Day -14 and up to 1st Follow-up Visit (or Early Termination), whichever is first –

- Dose increase and decrease in concomitant medication (see list in Protocol section 5.8.1) for glycemic control,
- Dose increase and decrease in concomitant lipid-modifying medications (see list in Protocol section 5.8.2).
- Dose increase and decrease in concomitant blood pressure management medications (see list in Protocol section 5.8.3).

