## 5.8. Concomitant Treatment(s)

Given the duration of the dosing phase in this study (ie, up to 16 weeks), *whenever possible*, attempts must be made to *not* alter the doses and regimens of the background/concomitant medications after randomization [ie, Visit 5 (Day 1)], and until Visit 12 (on-site Follow-up).

All concomitant medications taken during the study must be recorded with, at a minimum, the indication for use. In addition, for diabetes, lipid-modifying, BP control medications, daily dose, and start and stop dates of administration must also be captured. All subjects must be questioned about concomitant medication at each outpatient visit.

Medications taken within **6-weeks** before **Visit 5 (Day 1)** will be documented as a prior medication. Medications taken after dosing of double-blind IP at Visit 5 (Day 1) and until the 2nd Follow-up visit (or telephone contact) will be documented as concomitant medications.

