### 5.8.3. Medications for Controlling Blood Pressure

Across the many classes of agents for management of hypertension, subjects are permitted to be on stable doses of up to a **maximum of 3 agents**, starting at **≥ 8-weeks prior to Visit 1 (Screen 1)** and until Visit 12 (on-site Follow-up), across the country-specific, approved classes of agents;

- Starting at Visit 3 (Run-in), doses of medications (and additional medications can be added to a maximum of 3) in order to control BP and meet criteria needed to progress to randomization [refer to [Section 4.2](#), Exclusion Criterion 6].

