6.5.3 Concomitant Medications and Non-Drug Treatments

Number of subjects taking, at any time post randomization, medication affecting % liver fat (eg Vitamin E) will be tabulated by randomized arm.

Number of subjects under T2DM medication (T2DM), lipid medication, hypertension medication (HTN) will be tabulated by randomized arm.

For each category of medication (ie T2DM, lipid and HTN), the number of subjects receiving 0, 1, 2, or 3 medications will also be tabulated by randomized arm.

List of remaining concomitant drugs not part of the above list will only be listed.

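### SAP 3.4.3 pools up to two weeks of pre-randomization background-medication changes with on-treatment ones and, on its plain reading, leaves out agents started, stopped or switched

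*SAP*

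**What the plan says.** SAP 3.4.3 plans that "changes in background medications related to glycemic control, lipid control, or blood pressure will be summarized as follows, at any time after Day -14", running "up to 1st Follow-up Visit (or Early Termination), whichever is first". Three bullets follow:

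- "Dose increase and decrease in concomitant medication (see list in Protocol section 5.8.1) for glycemic control"
- "Dose increase and decrease in concomitant lipid-modifying medications"
- "Dose increase and decrease in concomitant blood pressure management medications"

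No other kind of change is named. The sentence does not itself say by arm; that comes from SAP 6.6.1, which summarizes safety data by randomized dose group unless noted otherwise.

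Under Protocol 4.3, subjects take single-blind placebo from Visit 4 (Day -14) and are randomized at Visit 5 (Day 1). Protocol 5.8 calls a medication concomitant once the Day 1 double-blind dose has been taken. It labels medications from the six weeks before Day 1 as prior. For blood pressure, Protocol 5.8.3 lets doses be changed from Visit 3, and says that "additional medications can be added to a maximum of 3", so that the subject can reach randomization.

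The nearest other summaries are in SAP 6.5.3: "Number of subjects taking, at any time post randomization, medication affecting % liver fat", and the number of subjects on 0, 1, 2 or 3 agents per class, by arm.

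**The concern.** A by-arm safety summary of medication changes should show whether investigators had to alter background therapy after treatment began, and in which arms. Two features of the rule work against that.

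First, the window opens before anyone is randomized. A change between Day -14 and Day 1 says nothing about the drug, yet it enters the same count as a change in Week 8. The SAP bullets also apply the word concomitant to an interval in which the protocol calls the same medications prior.

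Second, starting or stopping an agent is usually a larger change in background therapy than adjusting a dose. Triglyceride elevation is an identified adverse reaction (Protocol 1.4), and triglycerides, HbA1c and fasting glucose are endpoints. If agents acting on these were started or stopped at different rates across arms, a reader interpreting the endpoints would want to know.

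**Working it through.** The plan states no figure here, so there is none to reproduce. The check compares sections and does simple arithmetic on the window.

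**1. Share of the window before treatment.** Inputs: run-in placebo 14 ± 2 days (Protocol 4.3), dosing 108 ± 4 days (Protocol 3.1), 1st Follow-up 10 ± 4 days after last dose (Protocol 6.5). Share = pre / (pre + dosing + follow-up).

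- Nominal: 14 / (14 + 108 + 10) = 14/132 = 10.6%
- Smallest: 12 / (12 + 112 + 14) = 12/138 = 8.7%
- Largest: 16 / (16 + 104 + 6) = 16/126 = 12.7%
- Early termination after 28 days of dosing, with the visit 0 to 14 days after last dose: 14/42 = 33% down to 14/56 = 25%

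These are shares of days, not of changes.

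**2. Which classes can change between Day -14 and Day 1.**

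- Glycemic: Protocol 5.8.1 expects stable doses from at least 8 weeks before Visit 1. Changes should be rare.
- Lipid: Protocol 5.8.2 allows adjustment at Visit 3, then requires at least 6 weeks of stable dosing before Day 1. Changes should be rare.
- Blood pressure: Exclusion Criterion 6 directs that run-in be used to refine doses in subjects above its thresholds, and 5.8.3 allows additions. Run-in lasts at least 6 weeks (Protocol 1.3.1), and its last two weeks fall in the window.

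The pooling is therefore mainly a blood-pressure matter. The SAP lists the classes separately, so it would not carry over to the other two counts.

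**3. What pooling does to a comparison (assumed rates).** Let p be the proportion with a change after first dose and q the proportion with one before it, independent and with q equal across arms. The table shows P = 1 − (1 − q)(1 − p). Take p = 5% on placebo and 15% on an active dose:

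| q | Placebo | Active | Ratio | Difference (points) |
|---|---|---|---|---|
| 0% | 5.0% | 15.0% | 3.00 | 10.0 |
| 2% | 6.9% | 16.7% | 2.42 | 9.8 |
| 5% | 9.75% | 19.25% | 1.97 | 9.5 |
| 10% | 14.5% | 23.5% | 1.62 | 9.0 |

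The difference shrinks only by the factor (1 − q); the ratio falls faster. None of these rates is in the documents.

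**4. Whether starts and stops are counted.** The protocol treats them as separate from dose changes. Section 7.9.3 names new glycemic agents apart from dose changes, 5.8.3 names adding apart from adjusting, and the Appendix 4 checklist has separate boxes for dose increased, dose reduced, stopped temporarily and stopped permanently. SAP 3.4.3 takes up only the first two.

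**5. Whether another output recovers them.**

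- SAP 6.5.3 counts users and number of agents, with no timing and no comparison with baseline. A switch leaves the count unchanged.
- SAP 4.6.2 reviews changes made in violation of protocol. Protocol 5.8 asks for stability only where possible, so permitted changes fall outside that review.
- The concomitant-drug ANCOVA in SAP Appendix 1 uses presence or absence of a drug (SAP 5.2.1.4), not a change in it.

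None of these tabulates starts, stops or switches.

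**The case against.** The Day -14 start has a plausible reason. Baseline MRI-PDFF is taken between Visit 4 and Visit 5, other baselines fall back to Day -14 when Day 1 is missing (SAP 3.5), and the reporting window for baseline opens at Day -20 (SAP Appendix 2.1). A medication change on Day -10 may follow the baseline measurement and so bear on change from baseline. This stands. It is a reason to keep the interval visible, but not to merge it with the treatment period.

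The SAP also does not say that a start cannot be coded as an increase from zero, or a stop as a decrease to zero. That stands too: the omission is the plain reading, not a certainty. If either coding is possible, the term is undefined and needs a rule.

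A reader might go further and infer that investigators would answer rising triglycerides by adding a lipid agent, so that this table would hide a blunted drug effect. The documents do not support that. Protocol 5.8.2 expects stable lipid therapy to Visit 12, the visible action on triglycerides is withdrawal at a threshold (Protocol 3.2 and 7.9.2), and the content of Appendix 3 is not shown in the text available.

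**Conclusion.** The point holds as one of dilution and incomplete capture in a descriptive table. Up to two weeks of pre-randomization changes, mainly in blood-pressure drugs, are pooled with on-treatment changes. On the plain reading, agents started, stopped or switched are not counted in any class, and no other planned table in the unredacted text shows them.

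A reader might infer that the arms are compared with bias. They are not: changes before randomization balance across arms in expectation, so the effect is to blur a contrast and mislabel its timing. Nor is the primary analysis, an analysis set or the sample size touched.

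The size cannot be quantified from the documents. The 10.6% is a share of nominal days, and the ratios above rest on assumed rates. The omission of starts and stops is separate from the window and covers all three classes. It rests only on the wording of the bullets and on the protocol's own distinction between dose changes and other changes.

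**What to change.** In SAP 3.4.3, for each of the three classes and by randomized arm, tabulate the number of subjects with:

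- an agent started
- an agent stopped or switched
- a dose increased
- a dose decreased

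Count from the first double-blind dose on Day 1 to the 1st Follow-up or Early Termination. Show changes from Day -14 to Day 1 in a separate column, since baseline MRI falls in that interval. State how a stop and a start in the same class are paired as a switch, so that programmers do not have to decide.

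The cost is SAP wording and one larger table shell. Protocol 5.8 already requires daily dose and start and stop dates for these classes, so no new data are needed and no rule on medication use changes.

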3.5 Baseline Variables

For each subject, for each of the following parameters, baseline will be defined as:

- Liver fat content, via MRI-PDFF, defined as the value of total mean liver fat obtained between Visit 4 and Visit 5 (ie, labeled as baseline)

CCI

- Result closest prior to dosing on Day 1 [Visit 5] for the remaining pharmacodynamic endpoints **and all** safety-related continuous endpoints
 - As such would be results as reported on Day 1 [Visit 5], **and if these are not reported** would be the results reported on Day -14 [Visit 4]
 - If results on Day 1 [Visit 5] and on Day -14 [Visit 4] are missing the baseline will be considered as missing.

CCI

- For Adverse events, refer to definition of treatment-emergent outlined in Section 3.4.1, above

Change from baseline (CBL), relative change from baseline (RCBL) and percent change from baseline (PBL) will be calculated as follows:

- $CBL = \text{Observed Value} - \text{Baseline Value}$
- $RCBL = \text{Observed Value} / \text{Baseline Value}$
- $PBL = 100 \times (\text{Observed Value} - \text{Baseline Value}) / \text{Baseline Value}$

(NOTE: RCBL and PBL will not be considered for endpoints that can have a value of zero at baseline)

4 ANALYSIS SETS

Data for all subjects will be assessed to determine if subjects meet the criteria for inclusion in each analysis population set ***close (but prior to)*** database limit-write- access is achieved ***but prior to*** unblinding and releasing the database. Such classifications will be documented per standard operating procedures.

4.1 Full Analysis Set

This is the most inclusive subset of randomized subjects in a trial and is therefore compatible with Intention-to-Treat (ITT) analyses. This set includes all randomized

subjects who receive at least one dose of randomized study treatment (ie, on Day 1 [Visit 5]).

4.2 Per Protocol Analysis Set

The Per Protocol Analysis Set (PPAS) is a subset of the Full Analysis Set (FAS) excluding the following subjects **for the MMRM analysis on the primary efficacy endpoint:**

- Subjects with compliance, with randomized regimen administered (ie, relevant of the 3 bottles dispensed) over the entire treatment period, of less than 80%.
- Subjects with protocol deviation(s) deemed as compromising primary objective of the study (the list of subjects will be finalized close (but prior to) database limit-write- access is achieved but prior to unblinding and releasing the database).

For the Dose-Response analysis on the primary efficacy endpoint, PPAS is a subset of the FAS excluding the following subjects:

- Subjects with compliance, with randomized regimen administered (ie, relevant of the 3 bottles dispensed) over the entire treatment period, of less than 80%.
- Subjects with protocol deviation(s) deemed as compromising primary objective of the study (the list of subjects will be finalized close (but prior to) database limit-write- access is achieved but prior to unblinding and releasing the database).
- Subjects who withdraw during the randomized treatment period of the trial (post first dose on Day 1 [Visit 5] and before Week 16 [Visit 11]) and/or do not offer MRI (ie, not done or non-evaluable data) at Week 16 [Visit 11].

4.3 Safety Analysis Set

The safety analysis set is all subjects who receive at least one dose of randomized study treatment (ie, on Day 1 [Visit 5]).

4.4 Treatment Misallocations

In order to assess treatment misallocations drug dosing information will be collected. Treatment misallocations will be handled as follows. If a subject is:

Randomized but not treated, then the subject will be excluded from all the statistical analyses.

Randomized but took incorrect treatment, then the subject will be reported under his/her randomized group for all analyses that utilize the FAS and excluded from all statistical analyses that utilize the PPAS. The subject will be reported for safety and PK analysis under his/her actual randomized arm.

Treated but not randomized, then by definition they will be excluded from the efficacy analyses since randomized arm is missing, but will be reported under the dosing regimen they actually received for all safety CCI analyses.

4.5 Stratum Reassignment

Subjects who are randomized to the wrong stratum, in error, will have the incorrect stratum assignment remain in IMPALA but database (OCRDC) corrected based on following handling conventions:

Randomized but not treated, then the subject will be excluded from all the statistical analyses.

Randomized, treated, and took correct treatment, then the subject will be reassigned to and reported under the stratum he/she was supposed to be randomized to (and for which eligibility criteria are met) for all analyses (ie safety, CCI [REDACTED] and PD analysis) that utilize the FAS and the PPAS.

Randomized, treated but took incorrect treatment, then the subject will be reassigned to and reported under the stratum he/she was supposed to be randomized to for all analyses (ie safety, CCI [REDACTED] and PD analysis) that utilize the FAS and excluded from all statistical analyses that utilize the PPAS.

4.6 Protocol Deviations

The following sections describe any protocol deviations that relate to the statistical analyses.

It is possible that unexpected deviations will arise, becoming known only after the study has been active; hence more deviations may be added. A full list of protocol deviations for the study report will be compiled prior to database release.

4.6.1 Deviations Assessed Prior to Randomization

Granted exceptions to the inclusion or exclusion criteria are not expected to occur. Any subject who enters the study when the inclusion or exclusion criteria should have prevented entry will be considered to have had a protocol deviation. Whether such subjects will be excluded from FAS or PPAS will be determined as outlined in Sections 4.1 to 4.3, above.

4.6.2 Deviations Assessed Post-Randomization

All protocol deviations post-randomization will be reviewed and those that are thought to affect the primary objective/endpoint will be considered to define FAS and PPAS.

Examples of the protocol deviations assessed post randomization to assess for potential impact on the primary objective/endpoint include:

- subjects who receive excluded concomitant medications
- subjects whose background medications are changed in violation of protocol

- subjects who were randomized but took incorrect dosing regimen
- subjects whose overall (ie, over 16-weeks of dosing) compliance is below 80%

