#### 4.4.5. Confinement at Imaging facility

- Each outpatient visit to the Imaging facility (for MRI-PDFF) will occur following a fast (water permitted) of  $\geq 4$ -hours and same time of day ( $\pm 2$  hours) relative to MRI-PDFF completed at Visit 2 (Screen 2); refer to [Section 7.1](#) for additional details;
- Visits to Imaging facility can occur on the same day as the visit to the site either prior **or** after the Site visit;
- Visit to Imaging facility is also permitted to be on days separate from visits to site; but in this case must still occur within the pre-defined visit window [refer to [Schedule of Activities \(Table 1\)](#)].
- For assessment via FibroScan®, visits will occur either to the site **or** the Imaging facility – depending on where the FibroScan® device is located – however, the location of the device must be kept consistent at individual sites throughout the study execution;
- Similar to MRI-PDFF, each assessment via FibroScan® to occur following a fast (water permitted) of  $\geq 4$ -hours and same time of day ( $\pm 2$  hours) relative to FibroScan® assessment completed at Visit 1 (Screen 1).

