#### Withdrawal of consent:

Subjects who request to discontinue receipt of study treatment will remain in the study and must continue to be followed for protocol specified follow-up procedures. The only exception to this is when a subject specifically withdraws consent for any further contact with him or her or persons previously authorized by the subject to provide this information.

Subjects should notify the investigator in writing of the decision to withdraw consent from future follow-up, whenever possible. The withdrawal of consent should be explained in detail in the medical records by the investigator, as to whether the withdrawal is only from further receipt of investigational product or also from study procedures and/or posttreatment study follow-up, and entered on the appropriate CRF page. In the event that vital status (whether the subject is alive or dead) is being measured, publicly available information should be used to determine vital status only as appropriately directed in accordance with local law.

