Note regarding MRI windowing:

Subjects with MRI assessment up to a maximum of 48Hrs post last dose on Week 16 instead of 24Hrs post last dose on Week 16 as currently stated will be included in FAS and PPAS. This is to permit assessment of the primary endpoint while on drug.

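### SAP 4.6.2 lets post-randomization deviations be considered in defining the FAS, which contradicts SAP 4.1 and 4.4

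*SAP*

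**What the plan says.** SAP 4.1 sets one condition for a randomized subject to enter the FAS: at least one dose of randomized treatment. It adds: "This is the most inclusive subset of randomized subjects in a trial and is therefore compatible with Intention-to-Treat (ITT) analyses". SAP 6.1.1 makes the FAS the population for the primary MMRM, with the PPAS as sensitivity analysis. Protocol 9.2.1 likewise states the primary endpoint for the whole study population.

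SAP 4.6.2 says of protocol deviations after randomization that "those that are thought to affect the primary objective/endpoint will be considered to define FAS and PPAS". It gives four examples: excluded concomitant medication, "subjects whose background medications are changed in violation of protocol", an incorrect dosing regimen, and overall compliance below 80%.

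Three other sections bear on the same subjects. SAP 4.2 takes low compliance and deviations that compromise the primary objective out of the PPAS. SAP 4.4 keeps subjects who took the wrong treatment in the FAS under their randomized group and takes them out of the PPAS. SAP 4.5 does the same when the stratum was also wrong.

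The MRI windowing note in SAP 6.1.1 provides that "Subjects with MRI assessment up to a maximum of 48Hrs post last dose on Week 16", in place of the former 24 hours, are included in both the FAS and the PPAS, so that the endpoint is measured on drug.

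**The concern.** The FAS is meant to hold every dosed subject, whatever happens later. A clause that lets later events help define it gives the primary analysis set a second, narrower definition. The test in that clause is only that a deviation is thought to affect the endpoint; no criterion is given.

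Two things are at stake. First, a primary set pruned on post-randomization events is no longer protected by randomization, because such events can be consequences of treatment. Second, if the same deviations shape both sets, comparing FAS with PPAS says little about how sensitive the result is to those deviations.

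The MRI note raises a smaller, related question. It speaks of subjects, not scans, and does not say what happens beyond 48 hours.

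**Working it through.** **1. The plan's own numbers.** 60 completers per arm × 1.20 = 72 randomized per arm, and 5 × 72 = 360, as Protocol 9.1 states. The point does not depend on these figures and leaves them as they are.

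**2. The four examples in 4.6.2 against the other sections.**

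| Deviation | FAS under 4.1 | Specific rule elsewhere | 4.6.2 |
|---|---|---|---|
| Excluded medication | In, if dosed | 4.2: out of PPAS if judged to compromise the primary objective | May help define the FAS |
| Background medication changed against protocol | In, if dosed | 4.2: as above | May help define the FAS |
| Wrong regimen | In, if dosed | 4.4 and 4.5: stays in FAS, out of PPAS | May help define the FAS |
| Compliance below 80% | In, if dosed | 4.2: out of PPAS | May help define the FAS |

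In every row the subject already meets 4.1, and the PPAS consequence is already provided for. What 4.6.2 adds is a route out of the FAS. For the wrong regimen, that route conflicts with an express instruction in 4.4.

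**3. SAP 4.6.1.** This section on pre-randomization deviations also mentions exclusion from the FAS, but it refers back to 4.1-4.3, under which no dosed, randomized subject leaves the FAS. It is loose wording with no effect.

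**4. The MRI note.** A Week 16 scan more than 48 hours after the last dose is possible. Protocol 4.4.5 says "Visit to Imaging facility is also permitted to be on days separate from visits to site", within the visit window, and Protocol 6.6 says "Subjects who request to discontinue receipt of study treatment will remain in the study". The note can be read in two ways:

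- As set membership: a late scan puts the subject outside the FAS, losing up to 3 post-baseline scans (Weeks 4, 12 and 16).
- As a scan rule: only the late Week 16 value is lost, 1 scan.

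SAP 4.2 favours the scan rule. It excludes subjects lacking a Week 16 MRI only from the PPAS for the dose-response model and does not list them for the MMRM PPAS, so lacking a usable Week 16 scan is not in itself a bar to the MMRM.

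**5. Possible size.** The documents give no exclusion rate and no response profile for excluded subjects. Everything below is assumed, with exclusions in one active arm of 72 only.

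*Worse responders removed.* Shift = f × g, where f is the fraction removed and g is how many points worse their mean change is than that of subjects retained. With f = 0.10 and g = 10, 20, 30, the shift is 1.0, 2.0, 3.0 points towards the drug. If there is truly no effect, the one-sided error is 1 − Φ(1.2816 − f·g/SE), with SE = SD × √(1/72 + 1/(72(1 − f))). At SD = 30, SE = 30 × √(1/72 + 1/64.8) = 5.14, and the nominal 10% becomes 13.9%, 18.6%, 24.3%. Over f = 5% to 16.7%, the shift runs from 0.5 to 5.0 points and the error from about 12% to 37%.

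*Better responders removed.* Take a true 50% reduction, log-scale SD 0.45 and between-visit correlation 0.75, and drop the top 10% on a score correlated ρ with Week 4 response. The mean score falls by φ(1.2816)/0.90 = 0.1755/0.90 = 0.195 SD. The Week 16 shift is about 0.195 × ρ × 0.75 × 0.45 × 0.50. For ρ = 0.3, 0.5, 0.7 this is 1.0, 1.6, 2.3 points against the drug. A simulation of the same setting gave −48.6%, −48.3%, −47.5%, against −49.6% to −49.9% with everyone included. Keeping the removed subjects' Week 4 values in a likelihood fit returned the full-data result, since exclusion there depended on Week 4 response.

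*Similar subjects removed equally from every arm.* The shift is zero.

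**The case against.** The best defence is that 4.6.2 removes nobody. It says deviations will be considered, and the operative sections (4.1, 4.2, 4.4, 4.5) all keep dosed subjects in the FAS. SAP 4 fixes set membership before unblinding, and one rule serves all arms. On that view this is a stray word. Much of that stands: exclusion is permitted, not ordered, and no bias has been shown. It does not remove the conflict, because a team following 4.6.2 as written could take a subject out of the primary set. Blinding prevents deliberate selection, but not exclusions driven by events that treatment causes.

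A reader might infer three stronger things that the documents do not support.

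- **That subjects are removed selectively by arm.** Nothing says so. Protocol 1.2.2 and 1.3.3 report triglyceride rises in Phase 1 at 40 mg/day and above, and the top dose here is 50 mg, so a dose-related path through lipid-drug changes is conceivable. But Protocol 5.8 asks for stable background medication only where possible, so such a change need not be a violation. Protocol 1.2.2 also reports no apparent dose-related increase in adverse events.
- **That the MRI note drops anyone scanned after 48 hours.** It widens a limit and is silent beyond it. Protocol Table 1, footnote d, already calls for the Visit 11 scan within 24 hours of the previous dose, so later scans should be uncommon.
- **That the note penalises subjects who stay in follow-up compared with those who leave.** This needs the note to be a membership test for late scans but not for absent ones, and the text does not draw that distinction.

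**Conclusion.** The contradiction is in the text and rests on no assumption: 4.6.2 cannot stand beside 4.1 and 4.4, and 4.2 already does the work intended for the PPAS. If 4.6.2 were followed, judgement-based exclusions after randomization could enter the primary analysis set, and the PPAS would lose value as a contrast.

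The consequence is a risk, not an established bias. The illustrations in the working differ in sign according to who is removed, and they depend wholly on assumed rates, profiles and one-arm exclusion. For scale, the planned detectable effect in Protocol 9.1 is a placebo-adjusted change of at least 30%. The MRI note is a separate ambiguity that needs clarifying; it is not a second exclusion rule.

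**What to change.** - **SAP 4.6.2:** delete the reference to the FAS, so that deviations after randomization are considered only for the PPAS. Add that no protocol deviation removes a randomized, dosed subject from the FAS.
- **SAP 6.1.1, MRI note:** restate it by scan. A Week 16 MRI-PDFF value obtained more than 48 hours after the last dose does not enter the primary MMRM; the subject stays in the FAS with all other scans.
- **Optional:** remove the mention of the FAS in SAP 4.6.1, which is cosmetic, and add a supplementary MMRM using every scan obtained.

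The cost is a few sentences of SAP wording, settled before the analysis sets are classified, plus one output if the supplementary model is wanted. No new data are needed. The planned 72 per arm (360 in total), the one-sided 10% level and the model do not change.
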